The randomized repeated-measures design addresses threats to both internal and external validity and is strengthened by multiple replications (Shaddish, Cook, & Campbell, 2002). Caregivers will report treatments (i.e. medications) added during the 3 months to identify any potential influences. The Data Safety Monitoring panel will discuss new treatment developments and their impacts annually. Supervised training and monitoring protocols will assure fidelity. Measurement fidelity will be maintained by using measures with established reliability and validity and by research team training and monitoring. Research assistants (RAs) who code data will be blind to group assignment and video collection time to avoid expectation bias (Polit & Beck, 2007).

Aim 2. An exploratory descriptive design will identify PWD behaviors and precipitants captured in video that each caregiver identifies as their top priority. Content analysis and behavioral coding of videos will identify common behaviors (within the NDDCB framework), links to precipitants, and effective recommendations as a basis for a typology of caregiver interventions for in-home use (Dawson, et al., 1990). Actual caregiver use of interventions will be coded and audio recordings of team conferences will be transcribed and coded. Content analysis of this data will add information about characteristics predicting caregiver use of recommendations.

Aim 3. Caregiver satisfaction with effectiveness and ease of use will be evaluated and select caregivers will be interviewed and observed using FamTechCare. Video review team experts will rate the likelihood of diffusion into practice with a modified Duke Diffusion of Innovation in Long Term Care Battery (McConnell et al., 2010). Costs will be tabulated using traditional methods and compared to outcomes (PWD disruptive behavior and caregiver burden and NH placement intention), using traditional and Data-Envelopment Cost Analyses (DEA).

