Recording. Behavior Capture (see appendix E) was developed by Behavior Imaging with NIH SBIR support for monitoring children with autism. **Behavior Capture** uses a "go-back-in time" buffering technology to record when triggered, also capturing video up to 15 to 30 minutes prior to the trigger (we will use a 10 minute "go back" as was effective in our feasibility study). Including antecedents enables effective behavior assessment. **Behavior Connect** provides automatic Internet transfer of video recordings to HIPAA-secure storage.

Feasibility of using this new technology for the FamTechCare intervention was established with 5 caregiver-PWD dyads in our CTSA feasibility study (Williams et al., 2012). We will use and adapt as needed the IRB-approved protocols and procedures, protocols for encrypted HMU units and software configuration using Site Kiosk (a program that limits computer use to research-specific programs), contracts to assure HIPAA protections of video data, and training materials developed by our CTSA study team. Computers will be configured to run the high definition, wide-angle webcam and remote control with preset settings, eliminating the need for caregivers to login with names and password (avoiding added burden). HMU computers run

continuously, ready for caregivers to record when they want feedback by simply pressing a button on the remote control (that fits in a pocket or is worn around the neck). A 5-foot webcam extension cord extends the recording area and the laptop itself is portable and easy for caregivers to move. Although no password is required for the caregivers to start recording, each HMU will connect to a separate account for discreet storage requiring a logon password to limit access and protect confidentiality of the data.

Both groups will record behaviors during daily care for 3 months using a HMU. FamTechCare group videos will be immediately uploaded via the Internet to a HIPAA-secure site for expert team review and feedback in behavior management. The time and attention equivalent control group will receive only a weekly phone call from a nurse, but recorded videos will be held for review and feedback at 3 months. This encourages participation (all participants will benefit from expert video review and feedback during their study involvement).

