FamTechCare Intervention. The telehealth nurse will review videos submitted by caregivers within 24 hours to facilitate emergency referrals (delirium, for example). FamTechCare caregivers will receive same-day nurse feedback (using standardized interventions) based on evidence-based protocols (see appendix C) developed by team experts and in the feasibility study (Niedens, 2010; Williams et al., 2012). Individualized, contextually-based interventions developed by the expert team (see examples in appendix D) will be provided to caregivers in their home at least weekly (after each video review meeting).

The telehealth nurse will review and select videos, leading the interdisciplinary team meetings for video review and intervention planning and will interact weekly with caregivers to provide feedback. The internet-based team meetings will be conducted using Zoom HIPPA-secure teleconferencing that supports live, interactive videoconferencing from different locations. Zoom teleconferencing is accessed using a unique weblink to a secure meeting. Using a share screen feature, all group members can watch the videos and simultaneously discuss and develop interventions.

Interventions will be documented on a behavioral care plan form modeled after other studies, providing individualized intervention instructions for a specific disruptive behavior (Burgio et al., 2009). Interventions will initially focus on nonpharmacological interventions. For example, pain interventions may first focus on assisting PWD to report pain, identify person-specific indicators of pain for caregivers to monitor, and teach pain control measures such as relaxation, distraction, and massage to the family caregiver. Our interdisciplinary team includes clinicians and investigators from KUMC and UIHC in partnership with a social worker from the Alzheimer's Association, and home-care nurses. Additional experts, such as a pain management nurse and speech and occupational therapists are available as needed to review videos.

Control Intervention. The control intervention is designed to be equivalent to FamTechCare for time and attention. Control group videos will be held for review and feedback after 3 months. Control caregivers will receive a weekly phone call from the nurse, who will provide standardized disruptive behavior management guidelines per protocol (see appendix C) (Niedens, 2010).

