D7b. SPECIFIC AIM 2: Identify precursors of disruptive behaviors and develop a typology of interventions for caregiver in-home use. Recordings of team video review meetings will be transcribed and coded using qualitative content analysis to determine the most commonly occurring behaviors, precipitants, and recommended interventions within the NDDCB model framework. Interventions for each caregiver's three priority disruptive behaviors will be analyzed for effectiveness using our behavioral coding techniques (Williams et al., 2009). Patterns of disruptive behaviors in relation to antecedents and the caregiving context (i.e. lack of attention, interruption, overstimulation) will be coded using Noldus computer software based on Delgado's functional analysis system (2006). RAs (blinded to group and time of data collection) will code recordings for caregiver intervention use and disruptive target behaviors in PWD. Baseline and post-intervention data will be compared to determine the most utilized and effective interventions. Descriptive information (D6) about the dyad will be examined in relation to use of recommended interventions.

D7c. SPECIFIC AIM 3. Evaluate ease of use, satisfaction, and cost effectiveness of FamTechCare using traditional cost methods and Data Envelopment Cost-efficiency Analysis.

Ease of Use and Satisfaction. The Caregiver Satisfaction with Home Monitoring Survey (see appendix A) is a 12-item Likert checklist scale that ascertains ease of use and perceived satisfaction with the intervention. It will be completed at the end of the caregiver's study involvement. Descriptive results will be reported. In addition, our human factor expert will interview and observe five caregivers regarding FamTechCare HMU use.

Assessment of Diffusion of Innovation. The Duke Diffusion of Innovation in Long-Term Care Battery (Cain & Mittman, 2002; Kovach et al., 2008; McConnell et al., 2012; 2010) was adapted to assess critical factors determining likelihood of dissemination of the FamTechCare intervention into practice (see appendix B). The scale assesses perceptions of complexity, ease of use, compatibility with work practices, and observation. The dementia expert video reviewers will complete this questionnaire at the end of the study.

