The fixed effects in the model will include group (FamTechCare or control), site (UIHC or KU ADC), data collection time (baseline, 1, or 3 months), and all two-factor and three-factor interactions, including treatment by time interaction. A significant treatment by time interaction effect will indicate differences between the two groups. The analysis will be adjusted for important covariates, identified with baseline comparisons. With 70

subjects, 7 covariate factors meet statistical requirements for 5 to 10 subjects per covariate (Tabachnik & Fidell, 2001).

Fit of the models will be assessed using appropriate fit statistics, including Akaike information criterion (AIC) and likelihood ratio tests. To test for specific comparisons of interest, i.e. comparing treatment and control groups in terms of their mean change in PWD's disruptive behaviors, stress, and psychoactive medication use and caregivers' stress, burden, depression, sleep, and confidence (e.g., from baseline to month 3), tests of mean contrasts will be performed using parameter estimates from the fitted mixed models. Significant differences between the two groups, if they are in the expected direction, will support the hypothesis. An additional model per protocol will test changes in outcomes using only dyads in which the caregiver used recommended interventions in subsequent video recorded interactions.

D9b. Specific Aim 2. Identify precursors of disruptive behaviors and develop a typology of interventions for caregiver in-home use. We will use content analysis of caregiver submitted videos and recorded team video review meetings to tabulate the most common symptoms and behaviors. Qualitative content analysis of recorded team meetings for video review and written intervention plans for caregivers will identify key symptoms and behaviors. We will also code behaviors and symptoms exhibited by PWD in pre- and post-intervention videos submitted by caregivers. Counts will be analyzed descriptively to identify the most common symptoms and behaviors and the recommended interventions and their effectiveness.

D9c. Specific Aim 3. Evaluate ease of use, satisfaction, and cost effectiveness of FamTechCare using traditional cost methods and Data Envelopment Cost-efficiency Analysis (DEA).

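### Does the additional per-protocol model under Aim 1, limited to caregivers who used the advice, put the trial's main conclusion at risk?

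*Combined protocol and SAP*

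**What the plan says.** Section D9, Specific Aim 1, sets out a linear mixed model for repeated measures. Its fixed effects are group, site, time and all their interactions, and likelihood estimation keeps incompletely observed subjects in the analysis. Mean contrasts from the fitted models then compare the groups on change. The rule for the conclusion comes next: "Significant differences between the two groups, if they are in the expected direction, will support the hypothesis".

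Only after that does the plan add a further per-protocol model of changes in outcomes, "using only dyads in which the caregiver used recommended interventions in subsequent video recorded interactions". It gives no threshold for use and does not mention control dyads.

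Other sections bear on who would count as a user:

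- Section B, Aim 2, on the planned coding: "Content analysis of this data will add information about characteristics predicting caregiver use of recommendations". Section D7b adds: "Descriptive information (D6) about the dyad will be examined in relation to use of recommended interventions".
- Section D4 gives both arms standardized guidance from appendix C. Only FamTechCare caregivers also receive, before 3 months, feedback on their videos and "Individualized, contextually-based interventions developed by the expert team". In the control arm, "recorded videos will be held for review and feedback at 3 months".
- Section D7b has use and target behaviours coded by research assistants blind to group and time of collection.

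**The concern.** Randomisation makes the arms comparable as assigned. A subset defined by what caregivers did afterwards loses that protection. The plan itself looks for dyad characteristics that predict use, and section D6 collects much the same characteristics because they may influence outcomes. Users may therefore differ in prognosis from non-users. The advice also differs between arms, so a common filter may not select the same kind of dyad in each.

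Three readings are open: FamTechCare users against all controls, users against users, or users before and after. The first two can be biased. The third has no control group, and it follows behaviours chosen at entry because they were the most problematic, so some improvement could occur without any intervention effect. If the main result were null and this one significant, a reader might fear that the second would be presented as support for Aim 1.

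**Working it through.** **The plan's own figure.** Section D2 gives a difference of 29 points, SD 35, 35 dyads per group and a type I error of 0.05. Two-sided normal approximation: 29/35 = 0.829; divided by √(2/35) = 0.239 this is 3.466; 3.466 − 1.960 = 1.506; power = 93.4%, against 93% stated. The t-based value is 92.7%. The planned power reproduces, and the concern does not touch it.

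**Which result the support rule governs.** The order in D9 is mixed model, contrasts from the fitted models, support rule, additional model. The rule requires a difference between two groups. It therefore attaches to the contrasts just described, and it cannot be met by a before-and-after comparison among users.

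**How large the bias could be.** The documents give no use rate p and no correlation r between use and better change, so both are assumed. Suppose there is no true effect, change has unit SD, and use means that a latent score lies above its (1 − p) quantile z. The mean shift in a filtered arm is r·φ(z)/p; in an unfiltered arm it is 0. The values of φ(z)/p are:

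- p = 0.5: 0.399/0.5 = 0.798
- p = 0.7: 0.348/0.7 = 0.497
- p = 0.9: 0.175/0.9 = 0.195

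Type I error was simulated with 35 per arm, a pooled t test at two-sided 0.05, and 40,000 trials per setting.

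*Users against all controls*

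| r | Bias in SD at 50 / 70 / 90% use | Type I error |
|---|---|---|
| 0.1 | 0.08 / 0.05 / 0.02 | 5.9 / 5.3 / 5.1% |
| 0.3 | 0.24 / 0.15 / 0.06 | 12.7 / 8.6 / 5.4% |
| 0.5 | 0.40 / 0.25 / 0.10 | 27.1 / 15.4 / 7.0% |

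At r = 0.3 and 70% use, 0.149 × 35 = 5.2 points, taking the plan's SD as the SD of change. A more extreme corner, r = 0.5 with 40% use, gives about 17 points and 32% (20,000 trials). A negative r reverses the sign.

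*Users against users*

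- Equal use rates and equal r: bias 0, type I error 5%.
- 70% use in FamTechCare against 50% in controls: at r = 0.3 the bias is 0.3 × (0.497 − 0.798) = −0.09 SD; at r = 0.5 it is −0.15 SD. Type I error is 6.0% and 7.9%. With positive r this runs against FamTechCare; with negative r, in its favour.
- Equal rates, but r = 0.3 in FamTechCare and 0.1 in controls: bias 0.16, 0.10 and 0.04 SD at 50, 70 and 90% use; type I error 7.3, 6.4 and 5.2%.

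*Within users, r = 0.* If both arms improve by 0.2 SD for other reasons, users show significant improvement in 12.2, 15.4 or 19.3% of trials at 50, 70 or 90% use, against a nominal 2.5%. This is not false support under the stated rule, because no groups are compared.

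**Which reading fits.** The restriction to user dyads only is hard to square with keeping every control. Controls receive guidelines that they can use, and coders blind to group can code that use. Users against users is the more literal between-group reading, and it has the smaller biases.

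**The case for a change.** The strongest case for acting is that the plan nowhere calls this model exploratory or supportive and nowhere names the full randomised set as the basis for the Aim 1 conclusion. Use and disruptive behaviour are coded from the same recordings, and coding starts while enrolment continues, so a threshold could be settled with data in view. Plain wording would close these gaps at almost no cost.

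Much of this stands as fact. The selection is real, its sign is unknown, and blinding of coders does not set a threshold. Users against all controls cannot be ruled out either, since section D5 speaks of recordings repeated after FamTechCare interventions are used. But none of it alters the main analysis or the rule for the conclusion. The alternative of keeping only a before-and-after description of FamTechCare users would exchange a comparison with imperfect controls for one with none. That is a trade-off with no clear gain. Covariate adjustment in a model like the planned one could remove part of the selection, though not all of it.

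**Conclusion.** No change to the plan follows. Read in order, D9 rests the Aim 1 conclusion on group contrasts from the main mixed model; the per-protocol model is an extra whose limits are familiar to any trial statistician. Analysts can fill the gap by settling what counts as use and how it applies in each arm, reporting how many dyads qualify, and presenting the result as secondary.

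The possible distortion is confined to that extra model. Under the assumed inputs, type I error is 5% to 8% if both arms are filtered. It is about 9% in the middle case of users against all controls (r = 0.3, 70% use), and 27% to 32% only if a strong correlation of 0.5 coincides with use of 50% or less. All these figures rest on assumed use rates and correlations, normal outcomes and an unadjusted t test. The judgement would differ if the per-protocol result were used in place of the main contrasts, which the plan does not propose.

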D1. Sample. Eighty-eight dyads will be recruited from the University of Iowa Hospitals and Clinics (UIHC) and the University of Kansas Alzheimer's Disease Center (KU ADC). KU ADC is the area's major referral center with a clinic evaluating more than 300 new and 600 total patients annually. UIHC is the state and regional leader in tertiary care, providing research and clinical specialty care in Geriatric Psychiatry and Memory Disorders. It is estimated that 50% of family caregivers request professional assistance for managing disruptive behavior; so adequate study recruitment and enrollment is anticipated. If enrollment is not adequate, other dementia care providers (i.e. Alzheimer's Association) will be contacted.

Inclusion criteria for PWD are a diagnosis of AD or other dementia (moderate stage) and residing with a family caregiver who reports disruptive behavior management issues. Exclusion criteria include Huntington's disease, alcohol-related dementia, schizophrenia, manic-depressive disorder, deafness, and mental retardation. Participants with dementia of varied etiology will be included (a covariate factor). Electronic medical record search tools and dedicated research team time will facilitate identification of eligible participants. A trained research assistant (RA) will perform a Functional Assessment Staging of Dementia to confirm moderate dementia (Sclan & Reisberg, 1992) and the each caregiver will complete the Revised Memory and Problem Behavior Checklist (Roth et al., 2003) to verify the presence of disruptive behaviors on the initial home visit.

D2. Power. Sample size for this study was determined using power analysis for the primary hypothesis. The proposed sample size will provide sufficient power to detect between-group differences in outcomes (changes in proportions of behaviorally coded disruptive behaviors of PWD). In our previous research (Williams et al., 2009), the probability of PWD disruptive behaviors decreased from 55% to 26% when nurses used normal talk with PWD instead of elderspeak (patronizing communication similar to babble). We anticipate a similar 29% average decrease in the proportion of disruptive behaviors after the FamTechCare intervention. Applying this effect size as the difference between groups with a standard deviation of 35% in both and assigning a Type 1 error of 0.05 results in 93% power for detecting group differences after 3 months in 70 dyads (35 per group).

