We also estimate power for detecting between group differences in caregiver-reported burden and other outcomes (stress, sleep, depression, confidence in providing care and psychoactive drug use) at 1 and 3 months (adequate time to address multiple behaviors) using established standards for large (average .81) effect sizes across studies testing psycho-educational interventions like FamTechCare (Gallagher-Thompson & Coon, 2007). We assign a Type I error of 0.05 and assume a similar effect size (estimated between group differences). With average overall effect sizes of 0.81, there is 92% power for detecting differences in 70 dyads. Thus the study is adequately powered to detect outcome differences for PWD and their caregivers.

D3. Enrollment. We will enroll 88 dyads (44 dyads each in Intervention and Control) to compensate for 20% attrition over the 3-month study period, as seen in previous studies. We will enroll 8 subjects in each 3 to 4 month period, 4 at each site. This will be repeated in eleven cohorts (months 4 to 44) using staggered enrollment as part of a feasible implementation plan that rotates HMU units thus reducing equipment and personnel costs, while controlling for effects of history (see D10). Projected enrollment of 88 allows for up to 20% attrition providing a final N of 70 (35 per group) as required per our power analysis. Focus groups conducted during the feasibility study identified strategies to bolster enrollment in this study (dedicated provider recruitment time, multiple sites, and emphasis on ease of use and caregiver control of recordings [privacy]).

D4. Intervention. The multi component intervention includes 1) caregiver recording of symptoms and behaviors, 2) expert team review of recordings transferred via the Internet, and 3) feedback provided to caregivers at home. A HMU (iPod Touch or iPad Mini device) with Behavior Capture software and remote control will be placed in each home for 3 months. Limiting FamTechCare to 3 months is a limitation of this study as PWD develop new symptoms and behaviors as the disease progresses. However, in the feasibility study 3 months was adequate for caregivers to plateau in managing current disruptive behaviors. In practice, using the FamTechCare intervention at intervals as new behaviors develop and change over time may be more realistic.

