Cost Effectiveness Analysis We will focus on collecting accurate cost data for delivering FamTechCare, analyzing the effects of the intervention on costs, and calculating a simple cost-effectiveness ratio. We will use DEA to analyze the net effect of the intervention on costs (Hollingsworth, 2008). This approach tests the hypothesis that the cost of FamTechCare will be offset by reductions in PWD disruptive behavior and caregiver burden. We will calculate a simple cost-effectiveness ratio: the incremental cost of FamTechCare divided by reductions in caregiver desire for NH placement, using the 6-item Desire to Institutionalize Scale (Morycz, 1985) with reported reliability of 0.69 (McCaskill et al., 2010).

D8. Data Management. De-identified descriptive data will be labeled with each participant's unique identifier code and promptly transferred to data files in the REDCap platform. REDCap is managed by the Institute for Clinical and Translational Science, the University of Iowa's CTSA. In REDCap, primary data and data backups are secured in two separate data centers. Operating system security includes secure logins, remote system logging and configuration, and change management. Data encryption occurs both in flight and at rest and copies of data are replicated to the remote data center every 15 minutes to facilitate data recovery. Data will be entered in separate electronic spreadsheets using only identifier codes to assure confidentiality and anonymity (see Human Subjects). Only the research team will have access to the key for participant identification codes.

D9. Data Analyses.

Randomization. [name] will develop the randomization scheme using a 1:1 allocation ratio. For each site, random numbers will be generated to determine a sequence of dyad assignment to either control or treatment. To ensure equal numbers in each group, a blocking strategy will be used with blocks of 4 dyads.

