Cost Effectiveness Analysis (CEA) focuses on cost per unit change in PWD disruptive behavior (Δ PDB), comparing change in the proportion of disruptive behaviors between groups post-intervention. The additional costs for FamTechCare will be termed Δ C. For our CEA we calculate a 95% confidence interval for the ratio Δ C/ Δ PDB, defined as the change in cost per unit change in disruptive behaviors. Δ PDB will be modeled using the linear mixed model. At the end of the analysis we will generate a 95% confidence interval for a ratio, which can be complicated due to non-normality of the distribution of the parameter estimate. However, we will use a bootstrap procedure (Efron & Tibshirani, 1993) to alleviate this challenge. We will repeat this CEA using caregiver burden as the change unit. Our economist co-investigator has published on CEA (Lee, 2008).

Data Envelopment Analysis (DEA) is an ideal approach for assessing efficiency in this study. DEA allows consideration of multiple non-monetary outputs (Cooper et al., 2004; Hollingsworth et al., 1999; Seiford & Thrall, 1990) and uses linear programming to generate a coefficient of efficiency that compares cost factors to outcomes (Seiford & Ahn, 1993), with a large coefficient identifying efficiency. DEA compares cases with similar resources rather than the average or an artificial "ideal" (Charnes et al., 1994). DEA is a form of multi-attribute benchmarking used extensively in hospitals and NHs (Athanassopoulos et al., 1999; Chattopadhyay & Ray, 1996). Our health economist expert will fit a DEA model to investigate the overall efficiency in intervention compared to control in reducing caregiver desire for NH placement (Cooper, et al., 2004; Lee et al., 2009).

D10. Timeline. The initial 4 months of this 4-year study will be used to hire and train research team members in study protocols, to negotiate data protection agreements, and to purchase and configure equipment. The intervention and data collection will be completed in waves (8 participants every 3 to 4 months) during months 4 to 44. Analyses and coding will begin in the second half of year 01 and will continue through Year 04. Data analysis, dissemination and reporting will be completed in the final 6 months.

Research Study Activity	Year 1/Quarter				Year 2/Quarter				Year 3/Quarter				Year 4/Quarter			
	1	2	3	4	1	2	3	4	1	2	3	4	1	2	3	4

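### The bootstrap interval for the cost-effectiveness ratio has no provision for an effect interval that includes zero, and a percentile interval then misstates what the data allow

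*Combined protocol and SAP*

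**What the plan says.** Section D9c (Specific Aim 3) defines the cost-effectiveness result as ΔC/ΔPDB, the added cost of FamTechCare per unit change in the proportion of disruptive behavior, with ΔPDB taken from the linear mixed model. On uncertainty it says: "we will generate a 95% confidence interval for a ratio, which can be complicated due to non-normality of the distribution of the parameter estimate". The remedy is a bootstrap, with neither the type nor the resampling unit named. A second ratio follows: "We will repeat this CEA using caregiver burden as the change unit".

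The expected size of the two denominators is in D2. For behavior: "We anticipate a similar 29% average decrease in the proportion of disruptive behaviors after the FamTechCare intervention", used as the group difference with an SD of 35% in each arm, giving 93% power with 35 dyads per group. For burden and the other caregiver outcomes: "With average overall effect sizes of 0.81, there is 92% power for detecting differences in 70 dyads".

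Neither D7c nor D9c says what will be reported if the interval for the behavior or burden effect includes zero. There is no cost-effect plane, net benefit, acceptability curve or Fieller set, and no rule for bootstrap replicates with a negative or near-zero effect.

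**The concern.** The plan names the shape of the ratio's distribution as the difficulty. The harder difficulty is that the denominator can be zero. As the effect passes through zero, the ratio runs off to plus infinity and returns from minus infinity. Sorting such replicates and taking the 2.5th and 97.5th percentiles puts the least favorable results (a tiny benefit at a real cost) at the two ends of the list and joins those ends through zero.

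The published result would then be a wide interval containing zero. It would read as possibly no added cost per unit of benefit, when the data show only that the benefit is uncertain. A negative ratio is also ambiguous in itself: it can mean dearer and worse, or cheaper and better.

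**Working it through.** **Inputs from D2, D3 and D9.** Difference 29 points; SD 35 points in each arm; 35 analysed dyads per arm, after 20% attrition from 88; allocation 1:1; burden effect 0.81. A reduction in disruptive behavior is counted as positive. The documents give no costs, so every cost below is an assumption.

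**1. Reproduce the plan's power.**
- SE of the difference = 35 × √(2/35) = 8.37 points.
- 29/8.37 = 3.47, which gives two-sided power of 93.4% (noncentral t 92.7%). The plan states 93%. One-sided power would be 96.6%, so the plan's figure is two-sided.
- Burden: 0.81 × √(35/2) = 3.39, which gives 92.3% (t 91.6%). The plan states 92%.

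**2. When does the effect interval include zero?** When the observed difference is below 1.96 × 8.37 = 16.4 points (16.7 with t). No cost assumption enters. The probability is about Φ(1.96 − δ/8.37) for a true difference δ; at δ = 0 it is 95% by definition.

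| True difference | δ/SE | P(effect interval includes 0) | Percentile ratio interval spans both signs (simulated) |
|---|---|---|---|
| 29 | 3.47 | 7% | 7% |
| 19 | 2.27 | 38% | 36% |
| 14.5 | 1.73 | 59% | 59% |
| 0 | 0 | 95% | 94% |

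For burden at 0.81: Φ(1.96 − 3.39) = 7.7%, or 8.4% with t.

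The last column comes from trials with 35 dyads per arm and assumed per-dyad costs of 1500 (SD 600) versus 500 (SD 200), resampled within arm; Monte Carlo error is about one point. The last two columns nearly coincide because these are largely the same trials. With an assumed ΔC of 1000 (SD 300 per dyad), the ratio interval contained zero in 88% to 98% of trials whose effect interval included zero (true effects 29 to 5 points), and in at most 0.7% of the others.

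**3. What the interval then shows.** Take an observed effect of 10 points and assume ΔC = 1000, SD 300 per dyad.
- SE of ΔC = 300 × √(2/35) = 71.7, so the interval for ΔC is 1000 ± 143. Added cost is clearly positive.
- Effect interval: 10 ± 16.7 = −6.7 to 26.7.
- Percentile interval for the ratio: −847 to 990.
- Fieller set: the values r with A·r² − 20000·r + C ≤ 0, where A = 10² − 16.7² = −179 and C = 1000² − 143² ≈ 979,500. The roots are −149 and 37. Because A is negative, the set is everything below −149 or above 37.

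The percentile interval therefore includes all values from −149 to 37, zero among them, which the data exclude. It also stops at 990, although the compatible ratios have no upper bound. At an observed effect of 29 the two methods agree (21 to 80 against 21 to 82).

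**4. Net benefit in the same example.** With an assumed willingness-to-pay of 100 per point: 100 × 10 − 1000 = 0, SE = √(100² × 8.37² + 71.7²) = 840, interval −1676 to 1676. It is finite and has one reading. In simulation at an assumed 50 per point, bootstrap net-benefit intervals covered the true value in 93% to 95% of trials.

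**The case against.** The case for leaving the plan alone has real parts.

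- **Scope.** A reader might infer that Aim 3 as a whole fails when the effect is small. The documents do not support that. Process-based costing, the data envelopment analysis, the satisfaction survey, the interviews and observation, and the diffusion questionnaire (D7c, D9c) do not use this interval.
- **Frequency.** At the planned effect the problem is uncommon, about 7%. The larger shares need an effect well below the planned one. This stands, although D2 borrows the 29 points from nurses' communication with persons with dementia, and under D4 the control caregivers receive weekly nurse calls with behavior guidelines. A smaller difference is plausible.
- **Burden.** A reader might expect burden to be more exposed. The planned effects are nearly equal: 0.81 against 29/35 = 0.83.
- **Coverage.** It is tempting to say that the percentile limits mean nothing. They covered the true ratio in about 95% to 98% of simulated trials at effects of 5 to 29 points. The fault lies in which values the interval contains and omits, not in its overall coverage. The percentile method is itself an assumption, since the plan names no type.
- **Sign ambiguity.** Under the assumed costs no resample had a negative cost difference, so every negative ratio meant dearer and worse. The cheaper-and-better case is possible, since D7c anticipates offsetting savings, but it cannot be sized from the documents.

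None of this supplies the missing rule for an effect interval that includes zero.

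**Conclusion.** The point holds for the two ratio intervals in D9c, as a minor but real weakness of method. The bootstrap answers the difficulty that the plan names and leaves the more serious one open. At the planned effects this matters in about 7% of trials for behavior and 8% for burden, rising to more than a third at 19 points and more than half at 14.5.

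The 16.4-point threshold and the probabilities for the effect interval rest only on the plan's SD and sample size, treated as a two-sample comparison. The mixed model may give a different SE, and a larger SE would make the problem more frequent. The shares for the ratio interval and its width rest also on the assumed costs and on a percentile bootstrap.

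**What to change.** In D9c, specify one joint bootstrap of cost and effect that resamples dyads within arm, and name the bootstrap type. From those samples:

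1. Show the cost-effect plane in all cases, for behavior and for burden.
2. Report incremental net benefit (willingness-to-pay × effect − added cost) with bootstrap intervals over a willingness-to-pay range stated in advance, alongside the ratio's point estimate.
3. If an interval for the ratio is kept, use one that is valid when the effect may be zero, such as a Fieller set, and report it whatever its form.

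Do not make reporting of the ratio's interval depend on the effect interval excluding zero. That selects overestimated effects: among the percentile intervals that would be reported, simulated coverage fell to about 93% at a true effect of 14.5 points, roughly 85% at 10 and roughly 55% at 5.

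The cost is a little analysis code and no new data. A willingness-to-pay range per point of disruptive behavior and per point of burden must be chosen, because the documents give none.
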